2. LIST OF ABBREVIATIONS

| | |
|------------------------------------|--|
| AF | Atrial Fibrillation |
| AIC | Akaike Information Criterion |
| CHADS ₂ | Congestive heart failure, Hypertension, Age, Diabetes, Stroke(doubled) |
| CHA ₂ DS ₂ - | Cardiac failure or dysfunction, Hypertension, Age 75 (doubled), |
| VASc | Diabetes, Stroke (doubled) Vascular disease, Age 65-74 and Sex category (female) score |
| CHF | Congestive Heart Failure |
| CI | Confidence Interval |
| COPD | Chronic Obstructive Lung Disease |
| CT | Computed Tomography |
| DM | Diabetes Mellitus |
| DPC | Diagnosis Procedure Combination |
| HR | Hazard Ratio |
| ICD | International Classification of Diseases |
| ICH | Intracranial Hemorrhage |
| MDV | Medical Data Vision |
| MRI | Magnetic Resonance Imaging |
| NVAF | Non-Valvular Atrial Fibrillation |
| OAC | Oral Anticoagulants |
| PPV | Positive Predictive Value |
| PS | Propensity Score |
| PVD | Peripheral Vascular Disease |
| RR | Relative Risk |
| SD | Standard Deviation |
| SE | Systemic Embolism |

4. ABSTRACT

| | | | |
|---|-----------------------------------|---|---|
| Name of company: Boehringer Ingelheim | | | |
| Name of finished medicinal product: Prazaxa | | | |
| Name of active ingredient: Dabigatran etexilate | | | |
| Protocol date: 6 Jul 2017 | Study number: 1160.0288 | Version/Revision: Version 1.0 | Version/Revision date: Not applicable |
| Title of study: Comparative Effectiveness and Safety between Warfarin and Dabigatran Using Real World Claims data of Japanese Non-valvular Atrial Fibrillation Patients | | | |
| Rationale and background: Real-world data about the characteristics of patients with NVAF initiating an oral anticoagulant (OAC) in Japan has been scarce to date. The purpose of this study is to compare the effectiveness and safety of dabigatran and warfarin using the MDV database. | | | |
| Research question and objectives: To compare the effectiveness (stroke/SE) and safety (major bleeding) in patients with atrial fibrillation and newly treated with dabigatran and warfarin in the real world Japanese setting using a claims database | | | |
| Study design: A non-interventional study based on existing health insurance claims data | | | |
| Population: Medical Data Vision (MDV) clinical database is used. OAC-naïve, adult patients with NVAF initiating dabigatran or warfarin between 14 March 2011 (considering the launch date of dabigatran) and 30 June 2016 will be enrolled. Inclusion criteria: patients aged >18 year-old with confirmed diagnosis of NVAF (ICD 10 code I48), having a first prescription (index date) of either dabigatran or warfarin between 14 March 2011 to 30 June 2016, having no prescription of any OACs for 12 months prior to the index date (this period is defined as the baseline period). Exclusion criteria: patients having less than 12 months of enrolment prior to the index date, being dialysis or kidney transplant recipients in baseline period, having either atrial flutter, valvular AF, mechanical valve placement, rheumatic AF, and/or mitral valve prolapse/regurge/stenosis in baseline period, and having record of deep vein thrombosis or pulmonary embolism < 6 months before AF diagnosis in baseline period. | | | |
| Variables: Baseline characteristics of patients (age, sex, clinical history), year of initiating treatment, medical history, type of OAC and its dosage, concomitant medications, events related to stroke, systemic embolism, major bleeding, TIA, and myocardial infarction. | | | |
| Data sources: MDV clinical database. The database is health insurance claims database. As of end of February 2016, MDV provides commercial | | | |

| | | | |
|---|---|---|---|
| Name of company: Boehringer Ingelheim | | | |
| Name of finished medicinal product: Prazaxa | | | |
| Name of active ingredient: Dabigatran etexilate | | | |
| Protocol date: 6 Jul 2017 | Study number: 1160.0288 | Version/Revision: Version 1.0 | Version/Revision date: Not applicable |
| claims for in and out-patients consisting of medical records from more than 12.94 million patients from 230 large acute care DPC hospitals. . Observation period is planned from 14 March 2010 to 30 June 2016 considering the launch date of dabigatran. | | | |
| Study size: | The previous study 1160.279 was a feasibility study to look into the treatment pattern of OACs in Japan and internal validity of MDV database including availability of co-variates to conduct 1:1 PS matching. For warfarin and dabigatran comparison, the number of AF patients meeting inclusion and exclusion criteria after matching was 4,427 in each cohort. | | |
| Data analysis: | 
This study plans no formal hypothesis testing. The planned analyses are descriptive in nature and results are to be interpreted in an exploratory manner.
 
1:1 Propensity score matching (PSM) was conducted to address potential channelling bias. Outcomes will be assessed in the PSM sample.
 
Patient characteristics prior to and after propensity score matching will be described stratified by treatment group.
 
Patients will be followed up from treatment initiation (index date) to the day of treatment discontinuation (defined as a treatment gap longer than 14 days past the number of days of supply of the last prescription), the day before a switch to a different anticoagulant, the date of disenrollment in MDV, the end of the study period, the occurrence of the event of interest, or death of the patient, whichever occurs first (as-treated analysis).
 
Number of observed events, number of patient years, the corresponding incidence rates and their 95% confidence intervals (CIs) will be reported.
 
Dabigatran and warfarin outcomes will be compared by estimating the hazard ratios (HRs) for the outcomes and their CIs using Cox regression.
 
Kaplan-Meier curves for event-free survival will be estimated.
 | | |
| Milestones: | 
Start of Data Analysis: 1 July 2017
 
End of Data Analysis: 07 July 2017
 
Study Report: 18 August 2017
 | | |

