9.2 SETTING

MDV clinical database is used.

Definition

1. Index date: the date of first oral anticoagulant prescription, namely warfarin or dabigatran
2. Baseline period: 12 months prior to and including the index date
3. Drug exposure period: period of time from index date to the end of drug treatment determined by having continuous record of prescription with less than 14 days of gap in prescription (grace period) or by switching to another OAC (end of index treatment is then considered to occur the day before the prescription of the new OAC)
4. Follow-up period: the day after index date to the earliest of treatment discontinuation, day before switch, end of continuous enrolment in the database, end of study period or death.

Inclusion criteria

1. >18 year-old with confirmed diagnosis of non-valvular atrial fibrillation (NVAF, ICD 10 code I48)
2. New starters of dabigatran or warfarin

Proprietary confidential information © 2017 Boehringer Ingelheim International GmbH or one or more of its affiliated companies

3. No prescription of other OACs for 12 months prior to the index date, defined as the first prescription of OACs (the period is defined as baseline period)
4. Has an index date between 14th of March 2011 to 30 June 2016

Exclusion criteria

1. Having less than 12 months of enrolment prior to the index date
2. Dialysis or kidney transplant recipients in baseline period
3. Having atrial flutter, valvular AF, mechanical valve placement, rheumatic AF, mitral valve prolapse/regurge/stenosis in baseline period
4. Having record of deep vein thrombosis or pulmonary embolism <6 months before AF diagnosis in baseline period

The symptoms, diseases, or treatments in these criteria are defined by ICD-10 code, disease name, or medical care activity name (see Table 1).

Table 1

Definition of symptoms/diseases/treatment for inclusion/exclusion criteria

| Symptoms/diseases/treatment | Definition | | |
|-----------------------------|------------|----------------|--|
| | ICD10 code | Disease name | Medical care activity name |
| Dialysis | - | - | Including “dialysis” |
| Kidney transplant | T861, Z940 | - | - |
| Atrial flutter | - | Atrial flutter | - |
| Valvular AF | - | Valvular AF | - |
| Mechanical valve placement | T820 | - | Including “mechanical valve placement” |
| Rheumatic AF | I05-I09 | - | - |
| Mitral valve prolapse | I340 | - | - |
| Mitral valve regurge | I341 | - | - |
| Mitral valve stenosis | I050, I342 | - | - |

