9.3.2 Outcomes

9.3.2.1 Primary Outcome

- Outcome name: stroke and systemic embolism
- Time frame: drug exposure period
- Safety issue. N/A
- Definition: definition of stroke and systemic embolism provided in Koretsune et al will be used for this study⁸ as following.
 - ✓ Stroke: all three following conditions must be met:
 - [1] Imaging (magnetic resonance imaging (MRI) or computed tomography (CT)) is performed after a diagnosis code of atrial fibrillation.
 - [2] Diagnosis of stroke defined as I60-I64 occurs in the same month as the imaging
 - [3] Either of the following condition is met:
 - A) Rehabilitation for cerebrovascular disease within 30 days from the date of imaging
 - B) Death within 30 days from the date of imaging
 - ✓ Systemic embolism events:
 1. Retinal vascular occlusions: three following conditions must be met:
 - [1] Ophthalmic examination is performed after the date of definitive diagnosis of atrial fibrillation or cardioembolic stroke (including the day of the diagnosis).
The second or later ophthalmic examination during the same hospitalization is excluded.
 - [2] Diagnosis of retinal vascular occlusion in the month of the date of ophthalmic examination.
 - [3] The following A) and B) are satisfied:
 - A) Prescription of anticoagulant/antiplatelet agents on the day of ophthalmic examination or the next day
 - B) Non-prescription of anticoagulant/antiplatelet agents within 30 days from the date of ophthalmic examination.
 2. Other than retinal vascular occlusions: four following conditions must be met:
 - [1] Imaging: MRI, CT, roentgenography (using a contrast medium) or vascular echo is performed after the date of definitive diagnosis of atrial fibrillation or cardioembolic stroke (including the day of the diagnosis).
 - [2] Systemic embolism (including the name of injury/disease at the time of admission) is diagnosed and recorded as the name of the disease during hospitalization in the month of the date of imaging.
 - [3] The date of imaging or the next day: Treatment
Either of the following conditions is satisfied:
 - A) Treatment with heparin at >5,000 units or thrombectomy on the day of imaging or the next day
 - B) Death within 30 days from the date of imaging

✓ [4] Fees for emergency medicine administration or specific intensive care management on the day of imaging are calculated.

Intracranial bleeding: all four following conditions must be met:

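### Ending follow-up the day before a switch drops any event dated on the day another oral anticoagulant is prescribed, and the abstract and section 9.2 define a switch differently

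*Combined protocol and SAP*

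**What the plan says.** The abstract (Data analysis) lists several ends of follow-up. One is "the day before a switch to a different anticoagulant". The list closes with "the occurrence of the event of interest, or death of the patient, whichever occurs first (as-treated analysis", so the event is one stopping date among others and the earliest wins.

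Section 9.2, item 3, ends the drug exposure period at a prescription gap "or by switching to another OAC", and adds that "end of index treatment is then considered to occur the day before the prescription of the new OAC". Item 4 runs follow-up from "the day after index date to the earliest of treatment discontinuation, day before switch, end of continuous enrolment in the database", or to the end of the study or death if sooner.

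Sections 9.3.2.1 and 9.3.2.2 give both outcomes the same window: "Time frame: drug exposure period". That is the term defined in section 9.2.

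For systemic embolism other than retinal occlusion, section 9.3.2.1 asks for one of two treatment conditions. One is "Treatment with heparin at >5,000 units or thrombectomy on the day of imaging or the next day"; the other is death within 30 days of imaging. Table 3 codes heparin as ATC B01B.

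The visible text does not say which date is the event date (imaging, admission, diagnosis month, or the day the last condition is met). It also gives no rule for an event that falls on the day of a switch.

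**The concern.** A stroke, embolism or major bleed on the index drug is a reason to change that drug. When the change is made on the day of the event, the rule sets the end of exposure to the day before, and the event that prompted the change drops out. The censoring is then triggered by the outcome. The Cox model in section 9.7.1 contains treatment group only and assumes that censoring carries no information about the outcome, so it cannot correct for this.

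The incidence rates of both arms, which are planned outputs, would be too low. The hazard ratio would be biased if same-day switching after an event is more common in one arm. The arm that is switched more often would look better than it is.

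Separately, two definitions of a switch are in play. A programmer who follows the abstract could treat acute heparin as a switch; one who follows section 9.2 would not.

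**Working it through.** **1. Date logic.** Let the event be dated on day D. The visible text does not fix D; imaging day is assumed here, and admission day works the same way.

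| What happens | End of follow-up, abstract | End of follow-up, section 9.2 | Event on D counted? |
|---|---|---|---|
| Another oral anticoagulant prescribed on D | D−1 | D−1 | No, under either |
| Another oral anticoagulant prescribed on D+1 | D | D | Yes, under either |
| Heparin on D, no new oral agent | D−1 if heparin is a different anticoagulant | Not ended by heparin | No under the abstract, yes under 9.2 |
| Heparin on D+1, no new oral agent | D if heparin is a different anticoagulant | Not ended by heparin | Yes, under either |
| Thrombectomy or death, without heparin or a new oral agent | Not ended by a switch | Not ended by a switch | Yes, under either |
| Index drug stopped on D, nothing started | Gap rule applies | Gap rule applies | Yes, under either |

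Listing the event among the stopping dates does not help in the first row, because D−1 comes before D. If the event were dated by the last condition to be met (rehabilitation can fall up to 30 days after imaging), any oral switch between imaging and that date would also remove it.

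Retinal occlusion requires an anticoagulant or antiplatelet prescription on the examination day or the next. It is lost in the same way if that prescription is a new oral anticoagulant on the examination day.

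**2. Reproducing the plan's figures.** Inputs from section 9.5 and Table 9: 4421 per group, 0.40487 years, 0.03 events per year, margin 1.378, hazard ratio 0.716.

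- Pooled hazard ratio: exp(0.21 × ln 0.45 + 0.79 × ln 0.81) = 0.716, as stated.
- Warfarin events: 4421 × 0.40487 × 0.03 = 53.7.
- Dabigatran events: 53.7 × 0.716 = 38.4. Total D_tot = 92.1.
- Power = Φ( ln(1.378/HR) × √D_tot / 2 − 1.96 ). The hazard-ratio column of Table 9 cannot be read in the available copy. With 0.5, 0.6, 0.7, 0.8 and 0.9, the 0.03 rows give 0.995, 0.971, 0.899, 0.762 and 0.576, against the stated 0.996, 0.974, 0.905, 0.770 and 0.583. The event counts above are therefore a fair base.

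**3. Effect of lost events.** Let f_D and f_W be the fractions of dabigatran and warfarin events lost to a same-day switch. The documents give neither, so 5% to 20% is an assumption. The change in person-time is negligible (one day per switch).

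Observed HR = 0.716 × (1 − f_D) / (1 − f_W)

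| f_D | f_W | Observed HR |
|---|---|---|
| 10% | 5% | 0.716 × 0.90/0.95 = 0.678 |
| 20% | 10% | 0.716 × 0.80/0.90 = 0.636 |
| 20% | 5% | 0.716 × 0.80/0.95 = 0.603 |
| 5% | 10% | 0.716 × 0.95/0.90 = 0.756 |
| 10% | 20% | 0.716 × 0.90/0.80 = 0.806 |
| 5% | 20% | 0.716 × 0.95/0.80 = 0.850 |

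Equal loss of 5%, 10% or 20% leaves 0.716 unchanged. It cuts total events from 92.1 to 87.5, 82.9 or 73.7, and power at 0.716 from 0.881 to 0.865, 0.846 or 0.803. Each arm's rate falls by the same fraction: for warfarin, from 0.030 to 0.0285 per year at 5% and to 0.024 at 20%.

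**4. Against sampling error.** The standard error of ln HR is √(1/38.4 + 1/53.7) = 0.211. The 95% interval around 0.716 is 0.716 × exp(±1.96 × 0.211), or about 0.47 to 1.08.

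**The case against.** Stopping the day before a switch is a deliberate choice: it keeps events on the new drug's first day from being charged to the old one. The study is as-treated, descriptive and exploratory. A new oral agent may seldom be prescribed on the very day of a stroke or bleed, a switch one day later loses nothing, and the shifts above are small or moderate beside an interval of 0.47 to 1.08. All of this limits the size of the problem. It does not remove it, because the loss is systematic and follows from a written rule, and no visible passage exempts same-day events.

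Three stronger readings are tempting, and the documents do not support them.

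- *Heparin-treated embolism cannot be counted.* This follows only from the abstract's wording, and only for heparin on the event day. Section 9.2 defines the window for both outcomes and limits a switch to another oral anticoagulant, so heparin does not end exposure there. Calling acute heparin a switch is also a strained reading.
- *The bias favors dabigatran.* Nothing in the documents says which arm is switched more on the event day. Reversing the loss fractions moves the hazard ratio up instead of down.
- *Bleeds are generally lost.* A bleed is lost only if another oral anticoagulant replaces the index drug that day. If the drug is simply stopped, the 14-day gap rule applies and the bleed stays inside the window.

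**Conclusion.** The point holds in limited form. Under both the abstract and section 9.2, an event dated on the day another oral anticoagulant is prescribed is excluded by the stated rule, and the exclusion depends on the outcome. This rests on the event being dated by imaging or admission, which the plan leaves open.

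The direction of any bias in the hazard ratio is unknown. The range of 0.60 to 0.85 shows what 5% to 20% loss per arm would do; it is not a forecast. With about 38 and 54 events expected, 5% is roughly 2 or 3 events per arm and 20% roughly 8 or 11, so modest same-day switching is enough to matter.

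The heparin question is a wording conflict between the abstract and section 9.2 that must be reconciled, not an established loss of embolism events. The table of contents shows a redacted entry after section 9.7.1, so a sensitivity analysis on this point cannot be ruled out. It would not change the window set for the main analysis.

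**What to change.** - Bring the abstract into line with section 9.2, so that for censoring in the analysis only another oral anticoagulant is a switch. This is an analysis rule and has no bearing on treatment.
- State the event date for each outcome component.
- End follow-up on the date of the new oral anticoagulant prescription, and count an event dated that day for the index drug, ahead of censoring.
- Report by arm how many events fall on a switch date. This replaces the assumed 5% to 20% with data and shows whether the loss would have been unequal.

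The cost is a few words in the abstract and section 9.2, a line or two in section 9.3.2, and about one line of code. The downside is one day of possible overlap with the new drug, charged to the index drug. A sensitivity analysis that keeps the day-before rule would show whether that matters.

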5. AMENDMENTS AND UPDATES

| Number | Date | Section of study protocol | Amendment or update | Reason |
|---------------|-------------|----------------------------------|----------------------------|---------------|
| | None | | | |
| | | | | |
| | | | | |

6. MILESTONES

| Milestone | Planned Date |
|--------------------------------|---------------------|
| Start of data analysis | 18 July 2017 |
| End of data analysis | 21 July 2017 |
| Final report of study results: | 18 Aug 2017 |

7. RATIONALE AND BACKGROUND

Until 2002 in Japan, administrative claims data were not standardized or coded electronically. There was limited use for Health Authorities policy decision making or in health research (epidemiological, HTA). Ministry of Health, Labor and Welfare launched the Diagnosis Procedure Combination (DPC) system in 2002 linked with the reimbursement system. DPC is a Japanese version of the Diagnosis Related Groups system; such system is implemented in many countries including UK, US and Germany.

The DPC is a case-mix system, similar to Medicare in the US. It comprises of 18 Major Diagnosis Categories, 520 diagnostic groups and 2,658 case-mix groups. In the DPC algorithm, the diagnosis, procedure and comorbidities/complications are the 3 key variables for classification.

The diagnosis and comorbidities/complications are coded using the International Classification of Diseases (ICD) 10 scheme, while the procedures are coded using the Japanese Procedure Codes. Not only administrative claims data but also detailed patient data are collected for all the inpatients discharged from the participating hospitals. Dabigatran, first of the novel oral anticoagulants (OACs) to be approved and launched in Mar 2011 in Japan, was supported by the findings from the RE-LY study, which showed dabigatran efficacy in stroke reduction compared to warfarin with 150mg (relative risk (RR)=0.65, 95% CI = 0.52-0.81) and 110mg dose group (RR=0.90, 95% CI 0.74-1.10).¹ Major bleeding was also found to be reduced in the RE-LY study for both dose groups (110mg RR = 0.80, 95% CI 0.70-0.93), 150mg RR = 0.93, 95% CI = 0.81-1.07) compared to warfarin.

Several real world evidence studies have been published recently to compare effectiveness and safety of dabigatran, rivaroxaban and apixaban using claims database from the U.S., Danish and Taiwan national claims databases.²⁻⁵ In addition, several validation studies have been reported using DPC hospital claims database. Yamaguchi et al assessed the positive predictive value (PPV) of MDV claims defined event definitions for deep vein thrombosis, pulmonary embolism and bleeding events against clinical diagnosis of a panel of experts who examined claims codes and reached a consensus.⁶ Although sample of events were relatively small (50 for each event) PPV for thromboembolic events was 75% and bleeding events was 73.3%. Yamana et al evaluated the DPC data identified Charlson co-morbid conditions from 4 mid-size acute care hospitals against chart review diagnosis for the validity of claims defined diagnosis.⁷ Specificity was found to be over 96%, although sensitivity was below 50%. PPV for cerebrovascular disease diagnosis was reported to be 86.4% with negative predictive value of 93.5%. Koretsune et al conducted a validation study on MDV database to calculate the PPV for stroke, systemic embolism (SE) and intracranial hemorrhage (ICH) utilizing methodology similar to that reported by Yamaguchi et al, and found the PPV of stroke, SE events (SEE) and ICH to be 74%, 26.7% and 85.0%.⁸ Second evaluation of SEE after changing claims definition increased the PPV to 86.7%.

There has been no comparative effectiveness or safety analysis of dabigatran vs. warfarin has been published using large scale Japanese claims database thus far.

8. RESEARCH QUESTION AND OBJECTIVES

The primary objective is to compare the effectiveness (incidence of stroke/SE) in Japanese patients with atrial fibrillation and newly treated with either dabigatran or warfarin.

The secondary objective is to compare safety (incidence of major bleeding) in patients with atrial fibrillation and newly treated with dabigatran and warfarin in the real world Japanese setting using a claims database.

